#### 1.2 IMP 1: Pexa-Vec

#### 1.2.1 Pexa-Vec Description

Pexa-Vec (pexastimogene devacirepvec, JX-594) is an oncolytic and immunotherapeutic vaccinia virus engineered to express GM-CSF.

Pexa-Vec mechanisms-of-actions include tumor-cell infection and lysis (*Breitbach 2011; Kim 2006; Park 2008*), anti-tumor immune response induction (*Heo 2013; Kim 2013*) as well as acute vascular disruption (*Breitbach 2013*). Pexa-Vec is derived from the commonly used Wyeth vaccine strain (-Dryvax®, Wyeth laboratories).

Three genetic modifications are included in Pexa-Vec:

- 1. thymidine kinase (TK) gene deactivation,
- 2. GM-CSF gene insertion under the control of the synthetic early-late promoter, and
- 3. lac-Z gene insertion under control of the p7.5 promoter.

Selective targeting of tumor cells by Pexa-Vec is attributed to both engineered mechanisms as well as to inherent vaccinia selectivity for cancers (*Parato 2012*). TK gene inactivation renders viral replication dependent on the high cellular TK activity that is a hallmark of cancer cells (*Hengstschlager 1998*). Vaccinia vaccine strains have been shown to be inherently tumor targeting (*Thorne 2007; Yu 2004*). This may be attributable to the fact that many of the hallmarks of cancer (*Hanahan 2000*) (e.g., blocks in apoptotic pathways, dysregulation of cell cycle control and immune evasion) are also optimal cellular conditions for successful vaccinia virus replication. Furthermore, vaccinia replication and spread is dependent on epidermal growth factor receptor (EGFR) signaling (*Katsafanas 2004*), a pathway that is activated in most cancers (*Hanahan 2000*).

GM-CSF is reportedly an effective cytokine for stimulating tumor-specific anti-tumoral immunity (*Dranoff 1993*). Furthermore, the combination of vaccinia infection with GM-CSF production has been shown to result in enhanced efficacy in preclinical models, presumably due to additional immune stimulation due to GM-CSF expression within the tumor microenvironment (*Thorne 2007*). GM-CSF is also expressed by other oncolytic viruses like T-Vec (*Andtbacka 2015*) or Oncos-102 with efficacy demonstrated respectively in Phase III and in Phase I.

Protective anti-tumor immunity has been demonstrated following vaccinia infection of murine tumors in vivo (Kirn 2007). Pexa-Vec has also been shown to function as an immunotherapeutic in patients. GM-CSF expression was associated with increased neutrophil, monocyte and eosinophil production in Pexa-Vec treated patients (Breitbach 2011; Park 2008). Furthermore, inflammatory cell infiltration into tumors was also demonstrated with Pexa-Vec treatment (Hwang 2011; Mastrangelo 1999). Finally, functional anti-tumor antibodies mediating complement dependent cytotoxicity were induced after Pexa-Vec treatment of patients with liver tumors- (Heo 2013; Kim 2013).

Further information about the Investigational Medicinal Product (IMP) is available in the Investigator Brochure.

#### 1.2.2 Previous Pexa-Vec Non-Clinical Results

1.2.2.1 Efficacy of Pexa-Vec in Rabbit VX-2 Carcinoma Model and Rat Carcinogen-Induced Primary Liver Tumors

Efficacy of Pexa-Vec- as a single agent was studied in 2 liver cancer models.

hGM-CSF, expressed by Pexa-Vec is biologically active in rabbits, a species in which vaccinia virus replicates.

Accordingly, the virus was tested in the transplantable orthotopic rabbit carcinoma VX-2 model in which cells are implanted under the liver capsule forming liver tumors and metastases in liver and lung (*Kim 2006*). Tumor-bearing rabbits were treated with a single dose of 10^9 plaque forming units (pfu) of Pexa-Vec via IT or intravenous (IV) injection. Seven weeks post therapy, mean tumor volume in both Pexa-Vec treated groups was significantly smaller when compared to the phosphate buffered saline (PBS) control group. Furthermore, Pexa-Vec treatment prevented formation of metastases. Median survival time of rabbits in the PBS control group was 50 days while median survival was not reached in either Pexa-Vec treated group at 70 days

(*Kim 2006*). Rabbits treated with Pexa-Vec exhibited weight gain while control rabbits lost weight over the course of the study, presumably due to tumor progression. The dose response of the effects of Pexa-Vec treatment was determined by comparing the efficacy of a single IV dose of 10^8 pfu used in a subsequent study with the results discussed above with application of 10^9 pfu. Whereas a dose of 10^9 pfu resulted in 88% inhibition of primary tumor growth and 100% inhibition of metastases at 7 weeks, the lower dose of 10^8 pfu inhibited primary growth by only 10%, while inhibiting the incidence of metastases by 48%.

[figure not shown]
Pexa-Vec efficacy against primary liver tumors was investigated in an orthotopic primary liver tumor model. Cirrhosis and liver cancers were induced in rats by chronic oral administration of N-nitrosodiethylamine and N-nitrosomorpholine (*Kim 2006*). Tumor-bearing rats received 3 IV infusions of Pexa-Vec every 2 weeks. Over 10 weeks, 5 of 6 animals treated with Pexa-Vec exhibited complete responses by ultrasound while tumors in all PBS control animals increased in size.

[figure not shown]
These preclinical studies provide rationale for the use of Pexa-Vec as a novel therapy for HCC (refer to the IB for further details).

[figure not shown]

#### 1.2.3 Previous Pexa-Vec Clinical Results

As of February 2015, 1281 doses of Pexa-Vec have been administered by IT injection and/or IV infusion to more than 306 patients in 13 clinical research trials.

Overall, the clinical information available to date suggests that Pexa-Vec is safe at the clinical dose of  $10^9$  pfu when injected IT (*Kim 2006, Park 2008, Heo 2013*) and has not spread to caregivers in contact with the treated patients. For the previous clinical trials performed in France with Pexa-Vec as well as for the proposed study, the French Biosafety authority "Haut Conseil des Biotechnologies" classified Pexa-Vec for therapeutic use as a **GMO of Risk Level I** thus requiring specific rules and recommendations to be followed by caregivers. Preparation of viral solutions should be performed under a microbiological safety cabinet of type II using waterproof gloves, gown, surgical/procedure mask and safety goggles. All transfers of the preparation must be done within a sealed plastic transport bag or other sealed, leak-proof secondary container displaying a clearly marked biohazard symbol. All materials in contact with Pexa-Vec will be decontaminated and/or destroyed using hospital-grade chemical disinfectants active on vaccinia viruses.

[figure not shown]
## 1.2.3.3 Efficacy

Despite initial and potential transient tumor swelling due to edema and/or inflammation (termed as "oncolytic flare response" or "pseudoprogression"), Pexa-Vec has demonstrated antitumor activity as evidenced by decreased tumor enhancement and/or size on dynamic contrast-enhanced magnetic resonance imaging (MRI) or computed tomography (CT) based on RECIST 1.1 and/or mChoi and/or mRECIST for HCC criteria depending on the studies. Main activity / efficacy results from completed trials (n=12 trials) are summarized in the Table 3. Interestingly, distant tumor responses have been observed in distant, not injected, tumor lesions and this effect has been proved to be immune mediated (*Kim 2006, Heo 2013*).

In a randomized Phase II study (HEP007, NCT00554372) in advanced first line HCC a significant improvement of OS was observed with Pexa-Vec at  $10^9$  pfu (14.1 m) versus  $10^8$  pf (6.7 m) with a hazard ratio of 0.39 p = 0.020 (Heo 2013).

Pexa-Vec has now entered into a randomized, controlled Phase III trial in advanced first line HCC (NCT02562755), comparing the administration of Pexa-Vec and sorafenib to sorafenib alone with OS as primary endpoint.

Further information about the IMP is available in the Investigator Brochure.

# 1.3 IMP 2: Nivolumab (Opdivo®)

Nivolumab (Opdivo®) (also referred to as BMS-936558 or MDX1106) is a human monoclonal antibody (HuMAb; immunoglobulin G4 [IgG4]-S228P) that targets the programmed death-1 (PD-1) cluster of differentiation 279 (CD279) cell surface membrane receptor. PD-1 is a negative regulatory molecule expressed by activated T and B lymphocytes. Binding of PD-1 to its ligands, programmed death—ligands 1 (PD-L1) and 2 (PD-L2), results in the down-regulation of lymphocyte activation. Inhibition of the interaction between PD-1 and its ligands promotes immune responses and antigen-specific T-cell responses to both foreign antigens as well as self-antigens.

Nivolumab (Opdivo®) is approved in multiple countries including the US and Europe for the treatment of unresectable or metastatic melanoma in combination with ipilimumab (only in US) or alone for previously treated patients, and for the treatment of previously treated, metastatic non-small cell lung cancer (NSCLC) (only squamous form at present in the EU), for the treatment of previously treated advanced renal cell carcinoma (only in the US), for the treatment of advanced 2nd line squamous cell carcinoma of the head and neck (SCCHN) (US & Europe), for previously treated urothelial bladder cancer, and for classical Hodgins lymphoma. US nivolumab Prescribing Information (USPI) and EU nivolumab Summary of Product Characteristics (SmPC) are available on FDA and EMA websites, respectively.

#### 1.3.1 Nonclinical Studies

In addition, a comprehensive preclinical characterization of nivolumab was published in 2014 by *Wang et al.* Nivolumab binds to PD-1 with high affinity and specificity, and effectively inhibits the interaction between PD-1 and its ligands, PD-L1 and PD-L2, but not to related members of the CD28 family. In vitro assays demonstrated the ability of nivolumab to potently enhance T-cell responses, proliferation and cytokine production in the mixed lymphocyte reaction and superantigen or cytomegalovirus stimulation assays. No in vitro antibody-dependent cell-mediated or complement-dependent cytotoxicity was observed with the use of nivolumab and activated T cells as targets. Nivolumab treatment did not induce adverse immune-related events when given to cynomolgus macaques at high concentrations, independent of circulating anti-nivolumab antibodies where observed.

No studies have been performed to assess the potential of nivolumab for carcinogenicity or genotoxicity. Fertility studies have not been performed with nivolumab. In 1-month and 3-month repeat-dose toxicology studies in monkeys, there were no notable effects in the male and female reproductive organs; however, most animals in these studies were not sexually mature.

#### 1.3.2 Effects in Humans

#### 1.3.2.1 Pharmacokinetics

As further detailed in the SmPC, the PK of nivolumab was studied in patients over a dose range of 0.1 to 20 mg/kg administered as a single dose or as multiple doses of OPDIVO every 2 or 3 weeks. Based on a population pharmacokinetic (PK) analysis using data from 909 patients, the geometric mean (% coefficient of variation [CV%]) clearance (CL) is 9.5 mL/h (49.7%), geometric mean volume of distribution at steady state (Vss) is 8.0 L (30.4%), and geometric mean elimination half-life (t1/2) is 26.7 days (101%). Steady-state concentrations of nivolumab were reached by 12 weeks when administered at 3 mg/kg every 2 weeks, and systemic

accumulation was approximately 3-fold. The exposure to nivolumab increased dose proportionally over the dose range of to 10 mg/kg administered every 2 weeks.

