## 4.1 Inclusion criteria

Patients must satisfy all of the following criteria for entry into the protocol:

- 1. Male or female patients, age ≥18 years old,
- 2. Histological/cytological diagnosis of primary HCC, excluding cholangiocarcinoma, hepatocholangiocarcinoma, fibrolamellar carcinoma and hepatoblastoma. Note: if no previous pathological report is available, a tumor diagnostic biopsy should be performed,
- 3. Advanced stage HCC per EASL-EORTC (European Association for the Study of the Liver-European Organisation for Research and Treatment of Cancer) guidelines, i.e. patients who are not candidates for curative interventions and not candidates for locoregional modalities,
- 4. Patients naïve to systemic therapy for HCC,
- 5. Tumor status (as determined by radiology evaluation): At least one measurable viable tumor in the liver, ≥1 cm longest diameter (LD), using a dynamic imaging technique (arterial phase of triphasic computerized tomography [CT] scan, or dynamic contrastenhanced magnetic resonance imaging [MRI]), and injectable under imaging-guidance (CT or ultrasound),
- 6. At least one tumor that has not received prior local-regional treatment, or that has exhibited definitive growth of viable tumor since prior local-regional treatment of HCC undertaken at least 4 weeks prior to enrolment or 3 months prior to enrolment for radioembolization,
- 7. Child-Pugh Class A. Note: paracentesis, albumin infusion or diuretic treatment cannot be used to downgrade Child-Pugh score (e.g., to improve from severe to moderate/mild or from moderate to mild ascites),
- 8. Performance status 0 or 1 on the Eastern Cooperative Oncology Group (ECOG) scale,
- 9. Adequate hematological, hepatic, and renal function:
  - a. Hemoglobin ≥9 g/dL
  - b. Platelet count  $\geq 60 \cdot 10^9 / L$
  - c. International normalized ratio (INR) <1.7
  - d. White blood cell (WBC) count  $\geq 2.10^9/L$
  - e. Absolute neutrophil count (ANC)  $\geq 1.10^9/L$
  - f. Albumin ≥28 g/L, total bilirubin ≤1.5 times upper limit of normal (ULN); alanine aminotransferase (ALT), aspartate transaminase (AST) ≤5 ULN

- g. Serum creatinine <20 mg/L or creatinine clearance >60 mL/min according to Cockroft-Gault formula,
- 10. For patients who are sexually active: willing to use adequate barrier contraception method during Pexa-Vec and nivolumab treatment period, for at least 6 weeks after last Pexa-Vec injection and for at least 5 months after last nivolumab administration,

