# 8.12 28-day safety follow-up and end of study visit

The 28-day safety follow-up visit will be organized at least 28 days after the last treatment intake. In case of prior disease progression, this visit will be merged with the end of study visit. In case of treatment discontinuation without disease progression, the 28-day safety follow-up visit will be distinct from the end of study visit that will only occur after disease progression. In this case, patients will undergo in the meantime 6-weekly PFS follow-up visits. On both 28-day safety follow-up visit and end of study visit, patients will undergo:

- Complete physical examination, including weight, vital signs, and ECOG PS
- Skin and mucosal examination; reporting of AEs that occurred within 28 days of last study treatment administration and of concomitant medications, including potential anti-cancer therapies and significant non-drug therapies
- Blood sample collection for the following testing: hematology, chemistry, coagulation, CRP and thyroid blood tests
- Pregnancy test (urine) for WOCBP (if positive, an ultrasound will be performed to confirm pregnancy)

In addition, in the **phase I** part of the study, the following assessments will be performed:

- Cardiac echography (ECHO)
- Measurement of troponin levels
- 12-lead electrocardiogram (ECG).

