## 10.3 Time Period for Collection of AEs and SAEs

From the date of signature of ICF and up to first IMP administration (i.e. before the patient receives any IMP) only SARs caused by a protocol-required procedure (e.g., related to invasive procedures such as blood sampling) will be collected and reported (See sections 9.4 and 9.5). AEs, SAEs, or procedure related ARs that occur during this period, and that are considered by the investigator as relevant to the patient condition, will be collected as a current medical history.

After the initiation of either IMP and up to 28 days after the last dose of IMP, all AEs and SAEs should be collected and recorded on the eCRF. SAEs should also be reported to Transgene.

SAEs occurring more than 28 days after the last dose of IMP, and evaluated by the Investigator as related to the IMP should be collected and reported to Transgene indefinitely even after end of study. Only SAEs occurring prior to end of study will be reported in the eCRF.

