## **APPENDIX 3**

# GUIDANCE TO THE INVESTIGATOR IN CASE OF IMMUNE-RELATED AES

# **Gastrointestinal Toxicity**

Immune-mediated colitis has been associated with the administration of nivolumab. Diarrhea or colitis was reported in 21% of patients in two trials of nivolumab. Immune-mediated colitis occurred in 2.2% of patients in one trial- of these one patient had Grade 2 colitis, and five had Grade 3 colitis. In the other trial, Grade 3 immune-mediated colitis occurred in 0.9% of patients.

Patients should be advised to inform the investigator if any diarrhea occurs, even if it is mild. Range for time to onset of symptoms of colitis has been 1-6 months.

If the event is of significant duration or magnitude or is associated with signs of systemic inflammation or acute phase reactants (e.g. increased CRP or platelet count or bandemia), it is recommended that sigmoidoscopy (or colonoscopy, if appropriate) with colonic biopsy with three to five specimens for standard paraffin block be performed. If possible, one or two biopsy specimens should be snap frozen and stored.

[figure not shown]
Treatment may be restarted following the resolution of colitis. In addition, if the patient is being managed with corticosteroids, treatment should not be restarted until the steroids have been tapered down to a prednisone dose  $\leq 10$  mg/day. Patients who resume treatment should be monitored closely for signs of renewed diarrhea.

Table on next page provides a summary of dose modification guidelines for gastrointestinal toxicities.

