#### 8.8.1 Adverse Events

#### 8.8.1.1 Definitions

From the date of signature of ICF and up to first IMP administration (i.e. before the patient receives any IMP) only SARs caused by a protocol-required procedure (e.g., related to invasive procedures such as blood sampling) will be collected and reported. AEs, SAEs, or procedure related ARs that occur during this period, and that are considered by the investigator as relevant to the patient condition, will be collected as a current medical history.

After the initiation of either IMP and up to 28 days after the last dose of IMP, all AEs and SAEs will be collected and recorded on the eCRF. SAEs will also be reported to Transgene.

SAEs occurring more than 28 days after the last dose of IMP, and evaluated by the Investigator as related to the IMP will be collected and reported to Transgene indefinitely even after end of study. Only SAEs occurring prior to end of study will be reported in the eCRF.

All AEs will be coded using the Medical Dictionary for Regulatory Activities (MedDRA) central coding dictionary using latest version available. NCI-CTCAE version 4.03, dated June 14, 2010 will be used.

All AEs will be reported on the "Adverse Event" section of eCRF.

Dose-limiting toxicity (DLT) is defined as any of the following treatment-related adverse events (AEs) and occurring during the first 4 weeks (up to D29), in the Phase I part of the study; grades are referring to NCI CTCAE v. 4.03:

- 1. All Grade 3-4 non-hematologic toxicity that represent a 2-grade increase over baseline, excluding:
  - Untreated or inadequately treated nausea, vomiting and diarrhea,
  - Untreated or inadequately treated fever > 40.0°C lasting less than 24 hours (Grade
     3); only fever > 40.0°C lasting more than 24 hours (Grade 4) qualifies for DLT
  - Alopecia,
  - Grade 3 fatigue that returns to grade 2 or less within 7 days.
  - Grade 3 laboratory/metabolic abnormalities, other than ALT or AST, that are not considered clinically significant and that return to grade 2 or less within 72 hours.
- 2. Any Grade ≥ 3 treatment-related acute immune-related AE involving major organs, such as: immune-related pneumonitis, colitis, nephritis, hepatitis, endocrinopathies, immune-related rash and other rare but severe immune-related reactions.

- 3. Grade  $\geq$  3 injection site reaction.

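### Routine AE collection stops 28 days after the last dose, about one nivolumab half-life, so new non-serious immune-related AEs starting later are left out of the safety tables

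*Protocol*

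**What the plan says.** Protocol 10.3 sets the rule: after the first dose, "up to 28 days after the last dose of IMP, all AEs and SAEs should be collected and recorded on the eCRF". SAP 8.8.1.1 repeats it: "After the initiation of either IMP and up to 28 days after the last dose of IMP, all AEs and SAEs will be collected". Past 28 days, both documents collect only SAEs that the investigator attributes to study drug. These go to the sponsor with no time limit, but enter the eCRF only if they occur before the end of study.

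Protocol 8.12 applies the same limit at the 28-day safety visit and at the end-of-study visit, which require "reporting of AEs that occurred within 28 days of last study treatment administration". Both visits also include a physical examination and thyroid blood tests.

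The protocol uses longer horizons for nivolumab elsewhere:
- Section 1.3.2.1 (pharmacokinetics): "geometric mean elimination half-life (t1/2) is 26.7 days (101"%), the bracket being the coefficient of variation.
- Section 4.1, criterion 10 (contraception): "for at least 5 months after last nivolumab administration".
- Section 10.6 (pregnancy reporting): 3 months after the last dose.
- Appendix 3 (gastrointestinal toxicity): "Range for time to onset of symptoms of colitis has been 1-6 months".

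SAP 8.8.1.2 takes immune-related AEs from a tick-box in the eCRF. SAP 8.8.1.4 tabulates them alongside the Grade 3/4/5 events.

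**The concern.** Immune toxicity after a checkpoint antibody can appear after dosing has stopped, and this antibody clears slowly by the protocol's own figures. A window of one half-life closes while much of the drug is still present. Safety is the primary objective in Phase I and a secondary objective in Phase IIa.

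The gap is hardest to justify for patients who stop treatment without progression. Under Protocol 8.11 they return for imaging every 6 weeks (every 12 weeks after 12 months), count as active participants, and may not receive other anti-cancer treatment. Their end-of-study visit can come months after the last dose. A protocol thyroid test at that visit could reveal new Grade 2 hypothyroidism that the AE rule in 8.12 then excludes. Attribution is clearest in this group, so the information is being lost where it is easiest to interpret.

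The long-term follow-up in Protocol 8.14 does not fill the gap, because its AE trigger is limited to events related to Pexa-Vec.

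The study is small. With the planned maximum of 47 patients, one missed patient lowers an incidence by 1/47 = 2.1 percentage points. In a six-patient Phase I cohort it is 1/6 = 16.7 points.

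**Working it through.** **Inputs** (Protocol 1.3.2.1): half-life 26.7 days, coefficient of variation 101%; "clearance (CL) is 9.5 mL/h (49.7"%); "geometric mean volume of distribution at steady state (Vss) is 8.0 L (30.4"%); accumulation of about 3-fold on dosing every 2 weeks. The window is 28 days.

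**1. Does the stated half-life agree with the protocol's other figures?**
- Accumulation = 1/(1 − 0.5^(14/26.7)) = 3.28, consistent with about 3-fold.
- One-compartment check: clearance = 9.5 × 24/1000 = 0.228 L/day, and ln 2 × 8.0/0.228 = 24.3 days. This is close to 26.7; a terminal half-life need not equal this ratio.

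**2. How much drug remains when collection closes?**
- 28/26.7 = 1.05 half-lives, and 0.5^(28/26.7) = 0.483, or about 48%.
- Spread between patients, assuming a log-normal half-life: σ = √ln(1 + 1.01²) = 0.839. The quartiles of the half-life are 26.7 × exp(±0.674 × 0.839) = 15.2 and 47.0 days. Drug remaining at day 28 is then 28% and 66%.

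**3. What would other limits leave?**

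| Days after last dose | Basis | Drug remaining |
|---|---|---|
| 28 | current window | 48.3% |
| 90 | 3 months, as for pregnancy reporting | 9.7% |
| 133.5 | five half-lives | 3.1% |
| 152 | 5 months, as for contraception | 1.9% |

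**4. How does the window compare with the colitis range?** Appendix 3 states no time origin. Suppose the 1 to 6 months run from the first nivolumab dose (D15), with 30.4375 days per month as in SAP 7.7.2. The window closes (last dose day − 15 + 28) days after that first dose.

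| Last nivolumab dose | Window closes, months from first dose | Part of the 1–6 month range after closure |
|---|---|---|
| D29 | 42/30.4375 = 1.38 | (6 − 1.38)/5 = 92% |
| D43 | 56/30.4375 = 1.84 | 83% |
| D85 | 98/30.4375 = 3.22 | 56% |
| D127 | 140/30.4375 = 4.60 | 28% |

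The whole range is covered once first and last doses are at least 6 × 30.4375 − 28 = 154.6 days apart, about 22 weeks. These percentages are shares of a time range, not of events.

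**5. Which provisions capture a new event after day 28?**
- *Related SAE:* collected without time limit. Entry in the eCRF depends on what end of study means. The Definitions table makes it the last visit of the last patient in the trial, whereas 8.12 describes a patient-level visit that merges with the 28-day visit if progression has already occurred. On the patient-level reading, such an SAE reaches the sponsor but not the SAP tables.
- *Unrelated SAE:* excluded by 10.3. However, 10.5 requires any SAE during the course of the study to be reported.
- *Non-serious immune-related AE:* excluded by 10.3, 8.12 and SAP 8.8.1.1. However, 10.4 has AEs observed or mentioned at every study visit entered on the eCRF AE page.

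**The case against.** Several stronger readings are tempting, and the documents do not support them.

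- *All late immune toxicity is lost.* It is not. Related SAEs stay in scope indefinitely, and the definition in 10.1 includes medically important events without hospitalisation, so some late Grade 3 events would qualify. Under 10.4, related AEs and SAEs already open are followed until resolved, stable or back to baseline.
- *Late events at PFS visits can never be recorded.* This is too strong. Section 8.1 has patients asked about their health at each visit, and 10.4 points towards recording what is found. What stands is a conflict: 10.3 and 8.12 are the specific rules on timing, and a site following them would leave the event out.
- *Appendix 1 shows no AE assessment at PFS visits.* The extracted table is too damaged to show this. It also has no AE mark at the 28-day visit, where 8.12 plainly requires AE reporting.
- *Colitis mostly starts after the window.* Nothing says the 1 to 6 months run from the last dose. If they run from the first, much of the range falls on treatment for patients who continue, since dosing is every 2 weeks until progression and sometimes beyond. The 92% and 83% figures apply only to very early stoppers, whose number is not given.
- *48% of the drug remaining means 48% of the risk remaining.* No section links immune-related risk to remaining concentration.

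Two further points carry weight. Patients who stop for progression are to start sorafenib promptly (6.6.3), and the protocol describes its toxicity as significant, so late events there are hard to attribute. The 5-month figure comes from a contraception criterion and was not set as an AE window. Phase I de-escalation uses DLTs up to D29, so the 28-day post-dose limit does not alter that DLT count.

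**Conclusion.** The point holds in a limited form. As written, the plan closes routine AE collection at 1.05 nivolumab half-lives, with about 48% of the drug remaining (28% to 66% for the middle half of patients, if half-life is log-normal). New non-serious immune-related AEs starting later, and under 10.3 unrelated SAEs, do not reach the SAP 8.8.1.4 tables. Related SAEs are collected, but whether they enter the eCRF depends on an undefined use of end of study.

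The direction of the bias is clear: delayed immune toxicity is understated, more so in patients who stop early. Its size is unknown. The documents give no rate of late events, no distribution of treatment duration and no time origin for the colitis range. If that range runs from the first dose, patients dosed for about 22 weeks or more are fully covered for colitis.

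This is a completeness gap in a safety endpoint that is cheap to close, together with an internal inconsistency that needs resolving. It does not invalidate the safety analysis.

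**What to change.** 1. Amend Protocol 10.3, 8.11 and 8.12 and SAP 8.8.1.1 so that three classes of event starting more than 28 days after the last nivolumab dose go on the eCRF: immune-related AEs of any grade, AEs of Grade 3 or higher, and SAEs regardless of causality. Record them at the PFS and end-of-study visits already scheduled.
2. In 8.13, add one question on these events to the existing 8-weekly survival contacts.
3. State an upper limit and its basis, for example five half-lives (5 × 26.7 = 133.5, about 134 days) or the 5 months (about 152 days) already used for contraception. The two are not the same length, so name one.
4. Reconcile 10.4 and 10.5 with 10.3 and 8.12, so that sites have one rule on what is entered after day 28.
5. State whether end of study, for SAE entry in the eCRF, is the trial-level date or the patient's own visit.
6. In SAP 8.8.1.4, keep the 28-day tables as the main display and add a separate table for later events. Flag and tabulate separately those starting after a new anti-cancer therapy.

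The cost is protocol and SAP wording, a small eCRF change, possibly a consent update for the added question, and a few more AE forms. The downside is weaker attribution once another therapy has begun, which the flag makes visible but does not remove.
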